**NCT01930123**

## 1. Hypothesis and Principal Objective

### 1.1 Primary hypothesis

- Fructose is a risk factor for hepatic steatosis, NASH, and advanced fibrosis and that fructose exposure will worsen the metabolic, energy homeostatic and associated MR based biomarker associated features of nonalcoholic fatty liver disease (NAFLD).

### 1.2 Principal objectives:

- To define whether baseline and dynamic changes in hepatic ATP during a fructose challenge are associated with NAFLD and/or liver disease severity in patients with NAFLD.
- To assess whether such factors can be measured using magnetic resonance (MR) biomarkers

We will measure *baseline and dynamic* changes in metabolism, energy homeostasis and MR biomarkers in healthy volunteers and patients with biopsy-proven NAFLD. The effect of acute fructose challenges on changes in metabolism and energy homeostasis will be assessed in a cohort of patients with NAFLD.

## 2. Background and Significance

### 2.1 Prevalence of NAFLD

Nonalcoholic fatty liver disease (NAFLD) is now the most common liver disease in the United States and possibly worldwide (1). Nonalcoholic steatohepatitis (NASH), a more serious form of NAFLD, can progress to cirrhosis and even hepatocellular carcinoma (2). These liver diseases represent the hepatic component of the metabolic syndrome (3). The epidemic of NAFLD-related chronic liver disease has paralleled the rise in obesity world-wide.

### 2.2 Fructose as a Risk Factor for NAFLD

Like obesity, NAFLD and NASH are closely linked to nutrition and the “Western diet” which is rich in saturated fats and refined sugars. Although fat consumption has remained relatively stable, the marked increase in dietary fructose consumption (more than doubling in the past 30 years alone) supports the role of fructose in NAFLD and the metabolic syndrome (4-6). Although the mechanism(s) for fructose-related liver injury is not yet well defined, fructose-related hepatic adenosine triphosphate (ATP) depletion may contribute to liver injury. Observations in animals suggest that fructose induces metabolic syndrome and NAFLD independent of energy intake (7, 8). One key difference in fructose metabolism (as opposed to glucose) relates to ATP depletion and the necessity of adenosine monophosphate (AMP) kinase to replenish ATP stores. As opposed to glucose, initial fructose metabolism involves phosphorylation of fructose to fructose-1-phosphate by fructokinase (ketohexokinase, KHK) using the substrate ATP. Unlike glucokinase, the phosphorylation of fructose by KHK is specific for fructose and not rate limited (9). Replenishment of ATP stores requires phosphorylation of AMP back to ATP via AMP kinase (which is inhibited in insulin resistance (common *in patients with NAFLD*) or conversion to uric acid via xanthine dehydrogenase resulting in hyperuricemia.

The high activity of KHK in phosphorylating fructose to fructose-1-phosphate in the liver, could result in hepatic ATP depletion (10) with habitual fructose consumption.

Published animal and human studies support our hypothesis that fructose is a risk factor for NAFLD and NAFLD-related liver disease progression. In animal models, diets high in fructose induce features of the metabolic syndrome including weight gain, insulin resistance, hypertriglyceridemia, and hypertension (11). Similar effects are not observed with the administration of other simple sugars such as glucose (8). Fructose (or sucrose) administration to humans also causes features of metabolic syndrome (10, 12, 13) which are quite typical of patients with NAFLD. Fructose is lipogenic, stimulates triglyceride synthesis (14) and causes hepatic steatosis (15, 16). As previously reported in animals, our group reported that increased fructose consumption (assessed as fructose-containing beverages only) is a risk factor of metabolic syndrome and biopsy-proven NAFLD and that patients with NAFLD consume 3-4 times more fructose than age, gender, and mass index (BMI) matched controls without liver disease (17).

In addition to increased fructose consumption being a risk factor for NAFLD (17), *fructose has been implicated in NAFLD disease progression* (18, 19). The administration of a diet with 25% of total energy as sucrose (which contains 50% fructose) resulted in a rise in liver aminotransferase levels within 18 days (18). This study, performed nearly 25 years ago, is all the more alarming as current sugar intake of Americans is in this same range (4, 5). In our study of 427 patients with biopsy-proven NAFLD, increased consumption of fructose-containing beverages was univariately associated with decreased age ( $P < 0.0001$ ), male sex ( $P < 0.0001$ ), hypertriglyceridemia ( $P < 0.04$ ), low high density lipoprotein (HDL) cholesterol ( $<0.0001$ ), decreased serum glucose ( $P < 0.001$ ), increased calorie intake ( $P < 0.0001$ ), and hyperuricemia ( $P < 0.0001$ ) (19). After controlling for age, sex, BMI, and total calorie intake, daily fructose consumption was associated with *lower steatosis grade* and *higher fibrosis stage* ( $P < 0.05$  for each). Being that triglyceride synthesis requires ATP, we hypothesize that lower hepatic steatosis may reflect decreased ATP availability. Additionally, in older adults (age  $\geq 48$  years), daily fructose consumption was associated with increased hepatic inflammation ( $P < 0.05$ ), and hepatocyte ballooning ( $P < 0.05$ ) (19). However, the *mechanism(s) by which fructose causes liver injury remains unknown*.

### 2.3 Fructose Alters Energy Homoeostasis and Causes Hyperuricemia

[figure not shown]
In support of our hypothesis that ATP depletion underlies liver injury in patients with NAFLD, our group has demonstrated that patients with biopsy-proven NAFLD have increased hepatic mRNA expression of KHK compared to matched controls (17). Indeed, in human pilot studies, intravenous (IV) fructose administration is associated with hepatic ATP depletion (20, 21) which can be assessed by  $^{31}\text{P}$  magnetic resonance spectroscopy (MRS) (22). Reduced hepatic ATP stores are more prevalent in overweight and obese subjects than in lean subjects (23). Furthermore, recovery from fructose-induced ATP depletion was found to be delayed in patients with NAFLD ( $n=8$ ) (24). However, a limitation to this existing work is the small sample size and the inability to assess a cause-effect relationship(s) between BMI, NAFLD, energy homeostasis, and histologic features of liver injury. In liver cells, ATP depletion could perpetuate chronic liver injury by making fatty hepatocytes less proliferative. Hepatic ATP depletion also encourages the expansion of liver progenitor populations (25), causes arrest in protein synthesis, induces inflammatory and prooxidative changes (26, 27), increases endoplasmic reticulum stress, promotes activation of stress-related kinases, induces mitochondrial dysfunction, and increases

apoptotic activity (28-30). This supporting data suggests that fructose may be associated with NAFLD, NASH, and progressive fibrosis. Further, a study by Loguercio *et al.* demonstrated that increased uric acid levels above the basal level after IV fructose infusion was significantly higher ( $p < 0.01$ ) in patients with cirrhosis (3 mg/dl) and NASH (1.9 mg/dl) than in healthy controls (1.2 mg/dl) (31). This effect was completely reversed by fructose 1,6-diphosphate which could replenish the ability to resynthesize ATP from ADP. Therefore, an IV fructose challenge could effectively differentiate healthy subjects, from chronic hepatitis, from cirrhosis (31).

## 2.4 Hepatic ATP Depletion and Hyperuricemia as Potential Non-invasive Biomarkers for NAFLD

NAFLD lacks accurate and robust non-invasive biomarkers to grade and stage histologic disease activity. This is a critical barrier to understanding the influence of this important environmental risk factor (increased/habitual fructose consumption) on the pathogenesis and progression of NAFLD. Currently, reliable assessment NAFLD requires liver biopsy and interpretation of histology. Serum aminotransferase levels and conventional imaging methods can detect liver fat but cannot grade or stage NAFLD (32-35). Furthermore, current developments in biomarker are cross-sectional in nature and do not characterize the *dynamic* changes which underlie liver injury in patients with NAFLD. *In vivo*  $^{31}\text{P}$  MRS permits the evaluation of *dynamic changes* of individual phosphorus-containing metabolites in the liver parenchyma, such as phosphomonoester (PME), ATP, and inorganic phosphate (Pi). Intravenous fructose load alters phosphorus metabolites and allows assessment of liver function by  $^{31}\text{P}$  MRS (36). Other investigators have demonstrated that fructose loading could be used effectively as a tool to investigate change in metabolic steps of hepatic metabolism in humans with alcohol-related liver disease (36). Further, IV fructose loading causes significantly higher ATP degradation and uric acid production in cirrhotic patients than in healthy controls (36). The associations between fructose, increased uric acid, and hepatic ATP depletion has been previously described (14, 17, 19, 31, 36). Increased uric acid is an independent risk factor for NAFLD (37-41) and in keeping with our hypothesis, hyperuricemia may be a surrogate marker of impaired hepatic energy homeostasis in patients with NAFLD. The proposed mechanism for fructose-related hepatic ATP depletion, NAFLD, NASH and the associated hyperuricemia is depicted in Figure 1 is *novel, innovative, scientifically rigorous and address an important public health concern*—the impact of fructose on the rising epidemic of NAFLD.

Figure 1.  
Fructose Associated Hepatic ATP Depletion

For each fructose molecule that is metabolized, two molecules of ATP are consumed. The resultant ADP is then further degraded to AMP. The fate of this AMP is dictated by the relative activities of two competing enzymes, AMP kinase (AMPK) and xanthine dehydrogenase (XDH). When AMPK is more active than XDH, AMP is "recycled" to restore hepatocyte ATP content. Conversely, when XDH is more active than AMPK, AMP is converted to uric acid, delaying recovery of hepatic ATP stores. Insulin resistance, which decreases AMPK activity, further augments the effect of fructose metabolism, resulting in hepatic ATP depletion.

## 2.5 Use of MRI/ MRS as a Non-invasive Biomarker of NAFLD

Various MRI/MRS methods are used to investigate liver status (42-45). Tools used in this study will be extensions of these methods validated in other organs, and that we have adapted for use in the torso. All spectroscopy tools will use localized techniques, to provide volumetric hepatic metabolite measures. Hepatic energy homeostasis (ATP values) will be measured using an ultra-short TE sequence with “echo times” as short as 70  $\mu$ s, which increases the signal to noise ratio allowing shorter temporal sampling if needed. Hepatic lipid and water signals will be measured within a breath hold using  $^1\text{H}$  MRI sequences .

We will adapt the MRS acquisitions to provide a known reference against which to calibrate hepatic metabolite values. By calibrating the metabolites values, we will know exactly which metabolite(s) change and by how much, both within our cohort and in response to our dietary intervention study.

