### 3.2 Population

Participants at least 18 years of age, both healthy controls and those with suspected NAFLD.

**3.4 Sample size:** 30 healthy controls and 70 subjects with biopsy-proven NAFLD

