**10.1 Sample size and Statistical Power Consideration:** Assuming 20% change in hepatic ATP and uric acid (i.e. before~ Normal( $1.2, \sigma^2$ ) and after ~ Normal( $1, \sigma^2$ )), one-side test with alpha = 0.15, the power would be i) if  $\sigma^2 = 1$ , power = 0.523 ii) if  $\sigma^2 = 0.8$ , power = 0.629, iii) if  $\sigma^2 = 0.6$ , power = 0.784, iv) if  $\sigma^2 = 0.5$ , power = 0.875.

**10.2 Analytical and Statistical Approach:** We will test if the acute fructose challenge alters hepatic ATP in healthy volunteers compared to those with NAFLD and whether changes MR parameters and/or energy homeostasis can predict the histologic severity of NAFLD.

**10.3 Management of Missing data:** The occurrence of missing data in this trial is expected to be low. We estimate that careful selection of patients during the screening phase and the consent process should result in no more than 10% missing data from patients who drop out before completing the study.

**10.4 Justification of sample size:** A total of 67 patients will be included to compare the efficacy of acute fructose challenge on the metabolic and energy homeostasis changes in patients with NAFLD.

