## Appendix A:

### **MRI/MRS Protocols for Assessment of Energy Homeostasis and MR Biomarkers for NAFLD**

In all cases no patient repositioning will need to occur between data acquisitions for different MR nuclei. Primary measures are indicated in blue and include  $^1\text{H}$  MRI/MRS for water and fat measures and  $^{31}\text{P}$  UTE MRS for fructose measures. In all cases, the multiple acquisitions acquired prior to the injection of fructose will serve as test-retest cases for confirming measurement variance in the presence of pathology. Interleaved measures for experimental hypotheses may be moved or removed in order to ensure sufficient primary measures within the allotted MR time slot.

Only MR Slot 1 and Slot 2 protocols shown below will be used on the healthy volunteers for Aim 1 in order to optimize these protocols. The full MR protocol shown below will be performed for NAFLD subjects.

MR Slot 1 (Time 0)	MR Slot 2 (Post biopsy)
<math>^1\text{H}</math> MRI - anatomical $^1\text{H}$ MRI/MRS – water/fat $^{31}\text{P}$ UTE MRS – fructose baseline (multiple acquire) Fructose injection $^{31}\text{P}$ UTE MRS – fructose dynamic (multiple acquire) $^1\text{H}$ EPSI – water/fat $^{31}\text{P}$ UTE MRS – fructose dynamic (multiple acquire)	<math>^1\text{H}</math> MRI - anatomical for biopsy localization $^{31}\text{P}$ UTE MRS – fructose recovery (multiple acquire) $^1\text{H}$ MRI/MRS – water/fat

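### Baseline hepatic ATP and its absolute drop are not corrected for liver volume taken up by fat, so unless the calibration reference is tissue water, dilution alone lowers baseline ATP in NAFLD.

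*Combined protocol and SAP*

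**What the plan says.** All references are to the combined protocol and SAP.

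- **Objective.** Section 1.2 asks whether baseline hepatic ATP, as well as its change during the challenge, is associated with NAFLD and with its severity.
- **Measurement.** Section 2.5 describes volumetric metabolite measures from localized spectroscopy and states: "We will adapt the MRS acquisitions to provide a known reference against which to calibrate hepatic metabolite values". The kind of reference is not given. Section 4.1 describes the phosphorus sequence as run with the localization gradients left out. The coil-mounted phantom mentioned there serves to locate the coil.
- **Groups.** Section 3.4 plans "30 healthy controls and 70 subjects with biopsy-proven NAFLD". Section 8.2 requires controls to have no NAFLD on imaging or biopsy.
- **Analysis.** Section 10 defines baseline B as the mean pre-fructose metabolite value and D as B minus the minimum, an absolute drop. It also defines time to maximal change and time to recovery. The variance model has subject, voxel, scan and error terms only. Section 10.2 says "We will test if the acute fructose challenge alters hepatic ATP in healthy volunteers compared to those with NAFLD", adds prediction of histologic severity, and names no covariate.
- **Fat data.** Appendix A lists as primary the 1H "MRI/MRS for water and fat measures and" the 31P sequence. Water and fat are acquired in Slot 1 before fructose, with no repositioning between nuclei. No use of the fat signal to correct ATP is stated.

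**The concern.** A volumetric ATP value is ATP signal per unit of tissue sampled. Fat droplets displace ATP-containing tissue, so two livers with identical ATP in their fat-free tissue give different readings if their fat content differs. Fat content is what separates the two groups, and it varies within the NAFLD group.

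The analysis at stake is baseline ATP: healthy versus NAFLD, and against steatosis within NAFLD. A lower reading in NAFLD could be taken as impaired energy homeostasis when part or all of it is displaced volume. Within NAFLD the artefact makes ATP fall as steatosis rises. Section 2.2 expects the reverse ("we hypothesize that lower hepatic steatosis may reflect decreased ATP availability"), so dilution could also mask the relation that the protocol proposes.

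**Working it through.** **Inputs from the documents.** Mean ATP is 1.2 before and 1.0 after fructose, and the spread values are 1, 0.8, 0.6 and 0.5 (section 10.1, "Assuming 20% change in hepatic ATP and uric acid"). The test is "one-side test with alpha = 0.15" (10.1). The groups are 30 and 70 (3.4).

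**Assumptions, not in the documents.** Fat displaces fat-free tissue one for one; mean fat fraction is 3% in controls and 5% to 30% in NAFLD; the reference is not tissue water. Section 10.2 states no test level, so the 0.15 of 10.1 is borrowed.

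**Step 1: the plan's own power figures.** Section 10.1 prints powers of 0.523, 0.629, 0.784 and 0.875. A two-sample t test with 60 per group, difference 0.2 and one-sided 0.15 reproduces all four if the spread values are SDs. Read as variances, as printed, the same test gives 0.523, 0.574, 0.646 and 0.695. I therefore treat 1 to 0.5 as SDs. The figure of 60 per group is not stated; 60/(1 - 0.10) = 66.7 is consistent with "A total of 67 patients will be included" in 10.4, but not with a 30/70 split.

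**Step 2: dilution at baseline.** With equal ATP in fat-free tissue, the ratio NAFLD/control = (1 - fN)/(1 - fC). At 20% fat: 0.80/0.97 = 0.825, a 17.5% deficit, or 1.2 x 0.175 = 0.210 if controls read 1.2.

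**Step 3: chance of a positive baseline test from dilution alone.** SE = SD x sqrt(1/30 + 1/70) = 0.218 x SD. The chance is Phi(deficit/SE - 1.036). At 20% fat it is Phi(0.210/0.218 - 1.036) = 0.47 for SD 1, and Phi(0.210/0.109 - 1.036) = 0.81 for SD 0.5.

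| NAFLD fat | Ratio | Deficit | Deficit on 1.2 | Positive, SD 1 | Positive, SD 0.5 |
|---|---|---|---|---|---|
| 5% | 0.979 | 2.1% | 0.025 | 0.18 | 0.21 |
| 10% | 0.928 | 7.2% | 0.087 | 0.26 | 0.40 |
| 20% | 0.825 | 17.5% | 0.210 | 0.47 | 0.81 |
| 30% | 0.722 | 27.8% | 0.334 | 0.69 | 0.98 |

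The nominal rate is 0.15. If the smallest printed value is a variance (SD = sqrt(0.5) = 0.707), the last column becomes 0.32, 0.63 and 0.87 at 10%, 20% and 30% fat. These lie inside the ranges shown.

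**Step 4: the dynamic parameters.** Dilution multiplies a participant's whole curve by the same factor.

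- Absolute drop D: the same drop in fat-free tissue that reads 0.2 in a control reads 0.2 x 0.825 = 0.165 in NAFLD at 20% fat, 0.035 towards less depletion. At 10% it reads 0.186 and at 30% 0.144.
- Relative drop D/B: 0.165/(1.2 x 0.825) = 0.167, the same as 0.2/1.2 in controls.
- Time to minimum and time to recovery: scaling the curve does not move them.

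**The case against.** - **The reference may be tissue water.** If so, numerator and denominator both come from fat-free tissue and much of the dilution disappears. The documents do not exclude this. The bibliography lists papers on electronic-reference and synthetic-signal calibration, but the current text does not cite them, so they are only indicative. This stands: the point is conditional on the reference.
- **The primary outcome is dynamic.** Section 3.6 names the rate and extent of change. The relative drop and, in principle, the timings are untouched, and the bias in D is small and runs against the hypothesis. This stands, and limits the point mainly to baseline ATP, which 1.2 nevertheless makes an objective.
- **The fat fractions are assumed.** This stands. At 5% fat the effect is negligible.
- **The correction is not clean.** Sections 2.5 and 4.1 disagree on localization, so the liver fat fraction may not describe the volume that gave the phosphorus signal. If the fat fraction differs from the displaced volume, dividing by one minus it can create a spurious ATP-steatosis link, possibly in the direction that 2.2 expects. This stands, and is why the raw value must be kept.

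A reader might infer that dilution is as large as the planned effect, since 0.210 is close to 0.2. The documents do not support that comparison. The 0.2 in 10.1 is a before/after change, whereas dilution is a difference between groups at baseline, for which 10.1 plans no effect. The match also needs a NAFLD fat fraction near 19% with controls at 3%.

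**Conclusion.** The plan leaves a known source of bias in baseline ATP, and in D, while collecting the data needed to examine it. Unless the reference is tissue water, baseline ATP reads low in NAFLD by about 2% to 28% for assumed NAFLD fat of 5% to 30%. At 10% fat or more, the chance of a positive baseline test at one-sided 0.15 rises from the nominal 15% to between 26% and 98%, depending on fat and SD. These ranges rest on one-for-one displacement, 3% fat in controls, complete data and a normal approximation.

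They apply to the baseline comparison only. They are not error rates for the before/after change in 10.1 or for the test of response to the challenge in 10.2. Nor do the documents support saying that an association with severity in general is built in: the mechanism acts through steatosis, and the cohort described in 2.2 linked fructose intake to lower steatosis together with higher fibrosis. For an exploratory study this is a worthwhile, low-cost improvement that leaves the relative response to fructose intact.

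**What to change.** 1. In 2.5, 4.1 and 10, name the calibration reference and the resulting unit of ATP.
2. Reconcile 2.5 with 4.1 on whether the phosphorus acquisition is localized, and so which volume it samples.
3. If the reference is not tissue water, report baseline ATP per fat-free tissue, dividing by (1 - the participant's own Slot 1 pre-fructose fat fraction), beside the raw value in the healthy-NAFLD and severity analyses. Claim a baseline ATP association only if it persists after correction. If the reference is tissue water, say so and omit the division, which would then over-correct.
4. Report the drop also as D/B.

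**Cost.** No new scans or participants are needed, because the water and fat measures are already primary. The work is to settle the reference and the sampled volume and to add analysis wording. The fat measurement adds error to corrected ATP, and an imperfect match between fat fraction and displaced volume can induce some ATP-steatosis coupling. Showing both values lets a reader judge how far the conclusion depends on the correction.

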## 2.6. Summary

This study will advance several goals of the NIH Action Plan: 1) establish a multidisciplinary team to develop quantitative methodologies and imaging protocols for liver, 2) validate diagnostic criteria and methodologies for imaging in liver in both a cross-sectional and a longitudinal dietary intervention study of patients with NAFLD, 3) create a liver tissue bank with correlative imaging data, 4) develop reliable non-invasive MR markers to distinguish simple steatosis from NASH, and 5) define the *dynamic* changes in metabolism, energy homeostasis, and MR biomarkers as they relate to fructose-related liver injury.

## 3. Study design

### 3.1 Design overview

The proposed open label study is single-center randomized, phase II clinical trial designed to address the following specific aims:

- a) **To optimize an MR protocol to characterize the range and rates of *baseline and dynamic* measures of metabolism and energy homeostasis following an acute IV fructose challenge.** Volumetric and quantitative measures of hepatic lipid deposition, energy levels, and water homeostasis will be characterized in normal volunteers to determine typical ranges and coefficients of variation for each technique.
- b) **To differentiate the baseline and dynamic changes of metabolic and energy homeostasis following an acute IV fructose challenge in patients with biopsy-proven NAFLD.** MR-based measurements from the Aim 1 protocol will be correlated to clinical measures of metabolism, energy homeostasis and histologic disease activity before, during and at 4 and 24 hours following IV fructose challenge in regions co-localized and distant from biopsy.

A cohort study of healthy volunteers (n=30) and patients with NAFLD (n=70) will be enrolled. Healthy volunteers will have no evidence of chronic liver disease (normal liver enzymes and normal liver imaging and/or a liver biopsy performed for clinical evaluation of liver disease but whose pathology results note no pathologic abnormalities). Patients with suspected NAFLD who will undergo a standard-of-care liver biopsy, or who have had a historical biopsy within 6

months of the Screening visit, will have both acute intravenous fructose challenge for assessing baseline and post-dietary intervention *static and dynamic* measures of metabolism and energy homeostasis. Co-localization of liver biopsy with MRI to optimize / assess MRI measures of the histologic features of NAFLD will be performed to develop MRI as a surrogate “biomarker” for liver biopsy. With the exception of the liver biopsy, no accurate non-invasive biomarker for disease activity currently exists.

Screening for eligibility and collection of baseline data will span up to 8 weeks. Patients who have had a liver biopsy showing NAFLD within 6 months of the Screening visit or patients who will be undergoing a standard of care percutaneous liver biopsy for NAFLD will be consented.

Measures of acute changes in metabolism and energy homeostasis will be performed the morning of the liver biopsy. The primary comparisons will be made using an intention-to-treat analysis of the change in the (a) metabolic and (b) energy homeostatic measures from baseline. (c) compartment volumes by MRI. Secondary outcomes measures will include changes in clinical and histologic features of NAFLD as assessed by liver enzymes and the NAFLD Activity Score (NAS), as determined from standardized histologic scoring of liver biopsies. This study will be conducted in compliance with the protocol, Good Clinical Practice (GCP), and all applicable regulatory requirements.

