### 3.6 Outcome measures

#### *Acute Fructose Challenge and MR Biomarkers*

**Primary:** The difference(s) in rate and extent of the dynamic changes in metabolism and energy and water homeostasis in patients with biopsy-proven NAFLD. Liver histology will be the primary predictor of disease and the primary outcome variable to which secondary measures (i.e. MR-biomarkers, metabolic parameters etc) will be measured.

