## 9. Trial protocol—Study Visits and Events

### 9.1. Visit schedule overview

***Healthy controls*** will ONLY undergo:

- Screening for eligibility for enrollment (1-2 visits over a maximum of 8 weeks)
- Acute intravenous fructose challenge with measure of metabolism and energy homeostasis by magnetic resonance spectroscopy (MRS) (baseline and assessment of change over 60 minutes).
- MRI of the liver

Data collected from healthy controls will be used as reference and optimization values for which study will assess metabolic and energy homeostatic measures in those with NAFLD.

***Patients with NAFLD*** will undergo the following related activities study phases:

- Screening for eligibility for enrollment (1-2 visits over a maximum of 8 weeks)
- Acute intravenous fructose challenge with measure of metabolism and energy homeostasis by magnetic resonance spectroscopy (MRS) (baseline and assessment of change over 60 minutes. MRI of the liver

- Co-localization of non-invasive MR biomarkers with liver biopsy procedure.

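### Sections 3.1, 3.6 and 10.2 do not agree on the primary comparison, and the only test that is sized, a before-after change in NAFLD patients, does not address the first principal objective

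*Combined protocol and SAP*

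**What the plan says.** The first principal objective (section 1.2) is to find out whether baseline and dynamic "changes in hepatic ATP during a fructose challenge are associated with NAFLD and/or liver disease severity in patients with NAFLD". That is a question about a difference between groups, or about a gradient with severity.

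Four places bear on how it will be tested:

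- **Section 3.1** contains the only sentence that names the primary comparisons: "The primary comparisons will be made using an intention-to-treat analysis of the change in the (a) metabolic and (b) energy homeostatic measures from baseline". It gives no group, null hypothesis or test, and it lists changes in histologic features among the secondary outcomes.
- **Section 3.6**, under the label for the primary outcome: "The difference(s) in rate and extent of the dynamic changes in metabolism and energy and water homeostasis in patients with biopsy-proven NAFLD". It adds: "Liver histology will be the primary predictor of disease and the primary outcome variable".
- **Section 10.2**: "We will test if the acute fructose challenge alters hepatic ATP in healthy volunteers compared to those with NAFLD". It also plans to test whether the changes predict histologic severity.
- **Sections 10.1 and 10.4** give the sizing. Section 10.1 sets a before mean of 1.2 against an after mean of 1, one-sided at alpha 0.15. Section 10.4 counts 67 patients to "compare the efficacy of acute fructose challenge on the metabolic and energy homeostasis changes in patients with NAFLD" and mentions no healthy arm.

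Section 9.1 describes the healthy group's role this way: "Data collected from healthy controls will be used as reference and optimization values". Enrolment is 30 healthy controls and 70 NAFLD patients (sections 3.1, 3.4 and 8.1).

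**The concern.** Three sections give three accounts of what is primary, and the sized test matches only one reading of one of them. A before-after test in NAFLD patients has as its null that fructose changes nothing. The protocol's background already contradicts that null outside NAFLD. Section 2.3 reports a uric acid rise after IV fructose of 1.2 mg/dl in healthy controls, 1.9 in NASH and 3 in cirrhosis. Section 11.2.1 describes phosphate depletion and uric acid formation as general effects of fructose.

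Rejecting that null would show that the challenge worked. It would not show that the response differs in NAFLD or tracks severity. While the sections disagree, a significant before-after change could be reported as the primary success and read as support for the hypothesis, even if NAFLD livers behaved exactly like healthy ones.

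**Working it through.** **1. Reproduce the stated power.** Inputs from section 10.1: difference 0.2, one-sided alpha 0.15, variability values 1, 0.8, 0.6 and 0.5. From sections 10.4 and 10.3: 67 patients less 10% = 60.3, taken as 60. Two-sample noncentral t, 60 before and 60 after, noncentrality 0.2 / (SD × √(2/60)):

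| Calculation | 1 | 0.8 | 0.6 | 0.5 |
|---|---|---|---|---|
| Stated in 10.1 | 0.523 | 0.629 | 0.784 | 0.875 |
| 60 vs 60, listed value used as SD | 0.5225 | 0.6292 | 0.7838 | 0.8748 |
| 60 vs 60, listed value used as variance | 0.523 | 0.574 | 0.646 | 0.695 |
| 70 vs 30, listed value used as SD | 0.451 | 0.542 | 0.687 | 0.786 |

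The stated figures are those of a before-after comparison with 60 evaluable patients, before and after treated as independent, and with the values labelled as variances acting as SDs. A 70-versus-30 contrast does not give them. A one-group change in 30 subjects comes close (0.520, 0.626, 0.780, 0.872), but that too is a before-after test.

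**2. How often that test is positive if NAFLD patients respond exactly as healthy people do.** One-sample noncentral t, one-sided alpha 0.15.

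*Uric acid.* Common rise 1.2 mg/dl (section 2.3), n = 67, noncentrality 1.2 × √67 / SD. The documents give no SD of change, so a range is assumed. The test is taken in the direction of a rise, although 10.1 writes the ATP and uric acid change together as a fall.

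| Assumed SD of change (mg/dl) | 1 | 2 | 3 | 4 |
|---|---|---|---|---|
| Probability positive | >0.999 | >0.999 | 0.987 | 0.92 |

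*ATP.* The documents give no size for the healthy ATP response. Assume the planned 0.2 shift is common to everyone. SD of change = SD × √(2(1 − r)), where r is the before-after correlation.

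| | SD 1 | 0.8 | 0.6 | 0.5 |
|---|---|---|---|---|
| n = 60, r = 0 | 0.52 | 0.63 | 0.78 | 0.87 |
| n = 67, r = 0 | 0.55 | 0.66 | 0.81 | 0.90 |
| n = 67, r = 0.5 | 0.72 | 0.84 | 0.95 | 0.99 |

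Under the same condition a NAFLD-minus-healthy contrast would be positive 15% of the time, which is its alpha.

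**3. Power of the contrast that addresses the objective.** Difference in change, 70 NAFLD versus 30 healthy, one-sided 0.15, SD of change = SD × √2 (r = 0, as 10.1 implies). Normal approximation: Φ(difference / (SD × √2 × √(1/70 + 1/30)) − 1.036).

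| Healthy change | Difference | SD 1 | 0.8 | 0.6 | 0.5 |
|---|---|---|---|---|---|
| Zero | 0.2 | 0.349 | 0.410 | 0.517 | 0.602 |
| 63% of the NAFLD change | 0.2 × (1 − 1.2/1.9) = 0.074 | 0.213 | 0.230 | 0.262 | 0.288 |

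The 63% borrows the uric acid ratio 1.2/1.9 for ATP and is an assumption. Power for the association with histology cannot be computed: the plan gives no effect size, and section 8.2 lets some NAFLD patients enrol without a recent biopsy, so the number with usable histology is unknown.

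**The case against.** The strongest reply is that the disease contrasts are in the plan. Section 3.6 makes histology the primary predictor, 10.2 compares healthy volunteers with NAFLD patients, and aim b in 3.1 correlates the MR measures with histologic disease activity. The sentence in 3.1 names a variable and does not say that the test is within one group. Change from baseline is also what a between-group analysis would compare, and the reference to intention to treat suggests assigned groups. Section 10.4 neither uses the word primary nor refers to 3.1. Section 3.5 calls the study exploratory.

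Most of this stands. A reader might infer that the plan has no NAFLD contrast, or that its primary test must come out positive whatever NAFLD does. The documents support neither. The contrasts are planned, 3.1 can be read in two ways, and near-certain positivity holds only for uric acid under assumed SDs. For ATP, the measure in objective 1, section 2.4 implies some degradation in healthy controls but gives no size, so the ATP probabilities are conditional.

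The reply does not remove the disagreement. No section says which comparison is primary, and neither disease contrast has a power statement. The one calculation in the plan fits a before-after test and not 70 versus 30.

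**Conclusion.** The point holds as an inconsistency in the primary comparison combined with sizing for a test that does not address objective 1. It is conditional: the misreading arises if the before-after change in NAFLD patients is taken as primary, which 3.1 permits and 10.1 and 10.4 favour. In that case, with identical responses in NAFLD and health, the test would be positive with probability 0.92 to above 0.999 for uric acid (assumed SDs of 4 down to 1 mg/dl, n = 67). For ATP it would be about 0.52 to 0.90 at zero before-after correlation, if the planned shift is common to all. The contrast that does address the objective has power of about 0.35 to 0.60 under the favourable assumption of no healthy change, and about 0.21 to 0.29 under the borrowed uric acid ratio, against the stated 0.523 to 0.875. A higher before-after correlation than the zero implied by 10.1 would raise the power of both kinds of test.

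**What to change.** Make sections 3.1, 3.6, 10.1, 10.2 and 10.4 name the same primary contrasts:

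1. the NAFLD-minus-healthy difference in change from baseline, reported with an interval;
2. within biopsied NAFLD patients, the association of the change with histologic severity.

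State which comes first or how the two will be judged together. Keep the one-group before-after change only as a check that the challenge worked, and say that it supports no conclusion about NAFLD. In 10.1, replace the before-after power with power for the between-group contrast at 70 and 30, giving the assumed healthy change and before-after correlation and saying whether the variability values are SDs or variances. Add a precision statement for the histology association, based on the expected number of patients with usable biopsies.

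The cost is wording and a new power paragraph. No new patients or data are needed, since sections 5 and 9.1 already give the healthy controls the same challenge, spectra and blood samples. The downside is that the stated power becomes clearly less favourable.
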